No = 4, 3. Is your night slot No = 2, 4. State to what less Waist = 2, CRange of movem	Moder op distur Same el you es Xipho ent (les 0 - 30 - 31 -60 -61 - 90 -121 - 11	rate line bad by times – an use; id (ster ave this	your 1, your a num)	= 2, should mm fk = 4, he do 2 4 6	limit deler? (es = se pai N ector of pts pts pts pts	od by Se 0 nless, ock =	your pease for the pease for t	should mitati enably Hend crapis	der? on =1 setto = 8, or) (/4 behave	rities. Al	Tot 0 - 3 3:1 - 6:1 - 9:1 -	al (1 + 30 60 90 120	_	+ 4)			_ '
No = 4, 3. Is your night slot No = 2, 4. State to what less Waist = 2, CRange of movem	Moder p distur Some el you es Xipho 0-30 31-60 61-90 91-12	rate line bad by times – an use; id (ster ave this	your a num)	= 2, shou y rm fs - 4, he do	limit deler? (es = se pai N ector of pts pts pts pts	od by Se 0 nless, ock =	your pease for the pease for t	should mitati enably Hend crapis	der? on =1 setto = 8, or) (/4 behave	Allon:	Tot 0 - 31 - 61 - 91 -	al (1 + 30 60 90 120	_	1 + 4)			□ •
No = 4, 3. Is your night slot No = 2, 4. State to what leve Waist = 2, C Range of movem L FWD Flexion:	Moder op distur Some of you or Xipho on 10 - 30 - 31 - 60 - 90 - 12 121 - 11 > 150	rate line bad by times – an use; id (ster ave this	your a num)	= 2, should mm fk = 4, he do 2 4 6	limit deler? (es = se pai N ector of pts pts pts pts	od by Se 0 nless, ock =	your rease fo,	could residual to the could be	der? on =1 = 8, et) (/4	o rities. Al 900): Sen:	Tot 0 - 3 31 - 61 - 91 - 50 > 15	al (1 + 30 60 90 120	2+3		-		□ '
No = 4, 3. Is your night slee No = 2, 4. State to what less Waist = 2, C Range of movem L PWD Flexion: 3 External Rotati	Moder op distur Some of you or Xipho on 10 - 30 - 31 - 60 - 90 - 12 121 - 11 > 190 on :	rate limes thed by times — an use; id (ster ave this) 20	your 1, your a name) s for ti	1 = 2, shou 3 rm fs = 4, 6 0 2 4 6 10 p	limit lider? /cs = sr pai N sector i pts /pts /pts /pts /pts /pts /pts /pts	od by Se 0 nless, ock =	your rease fo,	cably Head erapis 2 - Al	der? on =1 - actio = 8, ot) (/4 behect	o rities. Al 900): Sen:	Tot 0 - 3 31 - 61 - 91 - 50 > 15	al (1 + 30 60 90 120	2+3				□ '
No = 4, 3. Is your night slee No = 2, 4. State to what less Waist = 2, C Range of movem 1 PWD Flexion: 3 External Rotati Hand behin	Modern pedisture Some of you or Xipho ocat (les 0 - 30 - 31 - 60 - 91 - 12 - 120 oca	tate limes thed by times the man use; id (ster mye this) 20 50	your a name) s for the	1 = 2, show y mm fix = 4, he do 0 2 4 6	limit dder? (cs = spain N setor : spts pts pts pts pts	od by Se 0 nless, ock =	your rease fo,	should mitati enably Head erapis 2 - Al	der? on =1 - actio = 8, or) (/4 - 1 - actio - 8, or) (/4 - 1	All of the control of	Tot 0 - 3 31 - 61 - 91 - 50 > 15	al (1 + 30 60 90 120	2+3				_
No = 4, 3. Is your night slee No = 2, 4. State to what less Waist = 2, C Range of movem L PWD Flexion: 3 External Rotati	Modern pedisture Some of you or Xipho ocat (los 0 - 30 - 50 - 90 - 12 121- 1: > 150 cm: d head & d hea	tate limes thed by times an use; id (ster ave this b) 20 50	your 1, your a nam) s for the story which the story that the story	1 = 2, show y mm fs = 4, the do 10 p	limit lider? /cs = sr pai N sector i pts /pts /pts /pts /pts /pts /pts /pts	od by Se 0 nless, ock =	your rease fo,	shouk erably Head erapis 2 - Al	der? on = active = 8, ot) (/4 beliert I all Rei	All of the control of	Tot 0 - 3 31 - 61 - 91 - 50 > 15	al (1 + 30 60 90 120	2+3			_	□ '
No = 4, 3. Is your night slee No = 2, 4. State to what leve Waist = 2, C Range of movem 1 PWD Flexion: 3 External Rotati Hand behin Hand behin	Modern p disture Same el you en Xipho ent (les 0 - 30 - 61 - 90 - 12 - 121 - 12 - 130 en: d hend & hend & hend & hend &	rate limes thed by times the true the rate the r	your 1, your a mann) 8 pts. 8 pts. 5 forwise we had	1 = 2, show y mm fit = 4, the do 0 2 4 6 10 p and 2 t	limit dder? (es = se poii N sector : s pts pts pts pts pts pts	od by Se 0 nless, ock =	your rease fo,	shouk mitati mabby Head erapis 2 - Al	der? on =1 - actio = 8, or) (/4 - 1 - actio - 8, or) (/4 - 1	000): All 1000): Latina ck	Tot 0 - 3 31 - 61 - 91 - 50 > 15	al (1 + 30 60 90 120	2 + 3			_	_ '
No = 4, 3. Is your night slee No = 2, 4. State to what leve Waist = 2, C Range of movem 1 PWD Flexion: 3 External Rotati Hand behin Hand behin Hand above	Modern p distur Some el you en Xipho ent (les 0 - 30 - 31 - 60 - 61 - 90 - 12 - 12 - 12 - 12 - 14 - 14 - 14 - 14	rate live bad by times - on use; id (ster ave this 0 50 50 c elbow c elbow c elbow	your 1, your a mann) 8 pts. 8 pts. 5 forwise we had	1 = 2, show y mm fit = 4, the do 0 2 4 6 10 p and 2 t	limit lider? (cs = repair N sector e pts pts pts pts pts	od by Se 0 nless, ock =	your rease fo,	should resistation and the second sec	der? on = active = 8, et) (/4 beliect I all Rei h.	000): All 1000): Latina ck	Tot 0 - 3 31 - 61 - 91 - 50 > 15	al (1 + 30 60 90 120	2 + 3 and to 2 4				 (
No = 4, 3. Is your night slee No = 2, 4. State to what leve Waist = 2, C Range of movem 1 PWD Flexion: 3 External Rotati Hand behin Hand above Hand above	Modern p distur Some el you en Xipho ent (les 0 - 30 - 31 - 60 - 61 - 90 - 12 - 12 - 12 - 12 - 14 - 14 - 14 - 14	rate live bad by times - on use; id (ster ave this 0 50 50 c elbow c elbow c elbow	your 1, your a mann) 8 pts. 8 pts. 5 forwise we had	1 = 2, show y mm fit = 4, the do 0 2 4 6 10 p and 2 t	limit lider? (cs = repair N N sector repair pts	od by Se 0 nless, ock =	your rease fo,	should resistation and the second sec	der? on = 1 activ = 8, rt) (/4 behact I suit Res b. Butto 81 join Waint	All Printers of the Control of the C	Tot 0 - 3 31 - 61 - 91 - 50 > 1; (Dot	al (1 + 30 60 90 120	2 + 3 and to 2 4 6	a)ı		_	□ •
No = 4, 3. Is your night also No = 2, 4. State to what leve Waist = 2, C Range of movem 1 FWD Flexion: 3 External Rotati Hand behin Hand behin Hand above Hand above Full elevation	Modern distart Samuel of you or Xiphos or 12 - 30 - 31 - 60 - 61 - 90 - 12 - 12 - 12 - 12 - 12 - 12 - 12 - 1	rate litres = an use; id (ster this bed) by times = an use; id (ster this bed) by the bed by the be	your a name) 8 pts foreither with the property of the proper	s = 2, show 3 mm fit = 4, he do 0 2 4 6 10 p and 2 k	lierait lider? (cs = sr pair N sector = sps pss pts pts pts pts 10	od by Se 0 nless, ock =	your interest literated by the second literated by the	should resistation and the second sec	der? on = 1 activ = 8, rt) (/4 behact I suit Res b. Butto 81 join Waint	All Printers of the Control of the C	Tot 0 - 3 31 - 61 - 91 - 50 > 1; (Dot	al (1 + 30 60 90 120 90 10 10	2 + 3 and to 2 4 6	a)ı		_	□ •
No = 4, 3. Is your night slot No = 2, 4. State to what leve Waist = 2, C Range of movem L FWD Flexion: 3 External Rotati Hand behin Hand behin Hand above Hand above Full elevation D Power (/25): Point	Modern distart Same et you en Xipho 0-30 31-60 61-90 91-12-1:> 150 km:d head & head & head & head & head & sa of arm	rate litres = an use; id (ster use this use;) 200 50 60 60 60 60 60 60 60 60 60 60 60 60 60	your a name) · s for the s	x = 2, shou y y em fix = 4, 6 10 p and 2 c and 2 x 2	lierait lider? les = repair N sector = repair pas	od by Se 0 nless, ock =	your rease fo,	should reinstation and the second sec	der? on =1 - action = 8, - st) (/4 behact 1 - Butto 81 join Wainst F12 Between	All on the constitutions of the constitution of the constitution of the constitution of the constitution of the co	Tot 0 - 3 31 - 61 - 91 - 50 > 1: (Dos	al (1 + 60 90 120 90 120 90 120 90 120 90 120	2 + 3 and to 2 4 6	a)ı		_	_
No = 4, 3. Is your night slee No = 2, 4. State to what less Waist = 2, C Range of movem 1 PWD Flexion: 3 External Rotati Hand behin Hand above Hand above Full elevation D Power (/25): Poir First pull: So	Modern distart Samuel of you or Xiphos or 12 - 30 - 31 - 60 - 61 - 90 - 12 - 12 - 12 - 12 - 12 - 12 - 12 - 1	rate litres = an use; id (ster use this use;) 200 50 60 60 60 60 60 60 60 60 60 60 60 60 60	your a name) · s for the s	x = 2, shou y y em fix = 4, 6 10 p and 2 c and 2 x 2	lierait lider? (cs = sr pair N sector = sps pss pts pts pts pts 10	od by Se 0 nless, ock =	your interest literated by the second literated by the	should resistation and the second sec	der? on =1 - action = 8, - st) (/4 behact 1 - Butto 81 join Wainst F12 Between	All on the constitutions of the constitution of the constitution of the constitution of the constitution of the co	Tot 0 - 3 31 - 61 - 91 - 50 > 1: (Dos	al (1 + 30 60 90 120 90 10 10	2 + 3 and to 2 4 6	a)ı		_	□ •
No = 4, 3. Is your night slot No = 2, 4. State to what leve Waist = 2, C Range of movem L FWD Flexion: 3 External Rotati Hand behin Hand behin Hand above Hand above Full elevation D Power (/25): Point	Modern distart Same et you en Xipho 0-30 31-60 61-90 91-12-1:> 150 km:d head & head & head & head & head & sa of arm	rate litres = an use; id (ster use this use;) 200 50 60 60 60 60 60 60 60 60 60 60 60 60 60	your a name) · s for the s	x = 2, shou y y em fix = 4, 6 10 p and 2 c and 2 x 2	lierait lider? les = repair N sector = repair pas	od by Se 0 nless, ock =	your interest literated by the second literated by the	should reinstation and the second sec	der? on =1 - action = 8, - st) (/4 behact 1 - Butto 81 join Wainst F12 Between	All on the constitutions of the constitution of the constitution of the constitution of the constitution of the co	Tot 0 - 3 31 - 61 - 91 - 50 > 1: (Dos	al (1 + 60 90 120 90 120 90 120 90 120 90 120	2 + 3 and to 2 4 6	a)ı		_	_

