To calculate the sample size, the prevalence of axillary network syndrome (AWS) described in the scientific literature was taken into account. It affects 30%. The 2020 records for patients who attended the Lymphedema Unit of A.G.S. Campo de Gibraltar Oeste has also been included adding 83 new patients. With these figures, a random sample of 46 individuals in total would be enough to estimate, with a 95% confidence and a precision of +-5 percent units, a population percentage of 10%.

SELECTION CRITERIA

Patients who meet all the inclusion criteria and no exclusion criteria will be included in this study prospectively.

INCLUSION CRITERIA

- Patient over 18 years old.
- Mastectomized patients (either radical or conservative surgery).
- Patient with lymphatic thrombus in the upper limb ipsilateral to the surgical intervention.

EXCLUSION CRITERIA

- Significant psychological alterations that would prevent the retrieval of the information necessary for the investigation.
- Significant neurological alterations that would prevent the retrieval of the information necessary for the investigation.
- Patients in a situation of legal dispute that would affect their intervention in this study.
- Metastasis not treated with chemotherapy treatment.

WITHDRAWAL CRITERIA

- Withdrawal of informed consent from the patient.
- Administrative decision taken by the researchers, promoter or a regulatory authority.
- Mild adverse event.
- Serious, unexpected or clinically relevant adverse event.

VALUATION CRITERIA

Main Variables:

- Mobility of the affected shoulder, measured by goniometry.
- Functionality assessment using the Constant and DASH scale (29,30).

Secondary variables:

Sociodemographic and clinical-surgical variables

- Age
- Marital status: married or in a common-law relationship, widowed, divorced or separated, single.
- Level of completed studies: illiterate, primary studies, secondary studies, university studies.
- Type of residence: in an urban / rural area.

- Children: yes / no.
- Mother after 30 years old: yes /no.
- Smoker: yes /no.
- Type of cancer. Four categories have been assessed: ductal, infiltrating, in situ, Paget's.
- Number of lymph nodes removed.
- Type of surgery (radical-conservative).
- Breast reconstruction (yes / no).
- Radiotherapy (yes / no).
- Time from surgery to the appearance of the Lymphatic Thrombus in days.

Clinical Variables:

- Visual Analog Pain Scale.
- Goniometry of all joints of the affected upper limb.

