- Record of daily performance of lymphedema prevention kinesitherapy since the operation (days per week / duration in minutes / day).
- Approximate time elapsed since breast cancer diagnosis: years. Date format dd / mm / yy will be included, if possible.
- Stage in which the cancer is found, according to the TNM scale.
- Body mass index.
- Creation of a scale to classify the type of lymphatic thrombus (based on its location, length, thickness, pain, functional limitation and whether it is palpable-visible or not).

Result Variables:

- Level of physical activity measured by the International Physical Activity Questionnaire.
- -Quality of life questionnaire EORTC QLQ-BR23

Employment and leisure Variables:

- Employment situation at the time of data collection: Four categories have been assessed: Active / Retired / Unemployed / Home worker.
- Sport practice: yes / no.
- Sport and frequency.

Description of the intervention

15 sessions of Assisted Passive Kinesitherapy are carried out by the physiotherapist. Five days a week, for three weeks. If it is previously referred, the treatment will be finished earlier (the patient must achieve the same ranges of motion and strength as the contralateral limb, together with the remission of pain).

The stretches applied during the sessions will be gentle and maintained, never exceeding a pain grade 5 VAS (moderate pain), once the tension of the cord is reached between 20-30 seconds. A special effort will be made to recover flexion and abduction of the shoulder, bringing the cord to a tolerable tension on the part of the patient.

Friction will be made on the axillary scar to dislodge underlying planes and the subcutaneous tissue of the muscle fascia.

The patient will be trained in active kinesitherapy to prevent lymphedema and activate lymphatic circulation. Also with hygienic-postural measures for the same purpose.

CONTROL GROUP

All the variables and data for each patients are recorded in their clinical history. Goniometric study will be performed of the affected upper limb (shoulder, elbow, wrist). Constant scale, Quick-Dash, the Visual Analog Pain Scale and the International Scale of Physical Activity will also be performed. This assessment will be carried out the patient arrives at our unit and on day 30, 60, 90.

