Axillary cord syndrome: It is a nominal qualitative variable. The presence of lymphatic cord was assessed by observation and palpitation by the assessor. Physical exam performed as suggested in previous researches: patient laying in supine position with elbow extended and the shoulder in maximum abduction. The assessor observes and palpates the beads, including the armpit, down the upper arm from the armpit to the antecubital space and through the forearm to the base of the thumb (34).

Range of motion: It is a continuous quantitative variable. For the assessment of the mobility goniometry has been used. Goniometer is the standard instrument for measuring the range of movement. The patients were asked to move thir arms in flexion, extension, abduction and external and internal rotation of the shoulder. It was considered that the maximum range of motion for the

flexion and abduction was 180°, for extension it was 45°, 100° for internal rotation and 80° for external rotation. Finally, a single index was calculated as the percentage of global movement (). Constant Scale: According to the Spanish Society for Shoulder and Elbow Surgery (SECHC), the Constant Scale assesses pain, functionality for daily life activities, joint mobility and shoulder strength. Also, it considers the laterality and the time it takes the patient. The score ranges from 0 points to 100 points, being 100 the optimal condition for the shoulder. (35, 37).

Quick-Dash (DASH): The Disabilities of the Hand, Arm and Shoulder (DASH) questionnaire is a specific instrument for measuring the quality of life related to health problems to the upper limbs. It is validated in Spanish and it consists of 30 questions. The final score calculation is relatively complicated. In order to calculate the scores it is necessary to have answered at least 27 out of the 30 questions. The final scores is obtained by calculating the arithmetic means of the questions answered minus 1 times 25. The DASH questionnaire has excellent reproductibility and high sensitivity, being able to detect small changes. The scale ranges from 30 to 150 points. 30 points means good shoulder functionality and 150 non-functional shoulder

It has two optional subsections where sports and work functionality can be assessed (38).

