For all study objectives in which two qualitative variables are related, the non-parametric Chi-square test will be used and, if necessary, the Fisher test will be used (in cases where the absolute frequency of more than 20% of the levels is less than 5 observations). To quantify the possible predisposing factors, the relative risk measures (RR), Odds ratio (OR) and their associated confidence interval will be obtained; Likewise, the sensitivity or specificity will be presented if it is considered necessary.

All analyzes will be accompanied by graphic representations for greater detail. Missing values will be those that are not completed.

All analyzes will be carried out with free R software and the significance level for all hypothesis testing is determined at 0.05.

WORKPLAN

The study will be carried out according to the following schedule:

Development and approval of the Provincial CEIC

OCTOBER 2021

Beginning of the recruitment period and action on the intervention group

DECEMBER 2021

Drafting of results, discussion and conclusions of the project

DECEMBER 2023

According to the schedule set forth, the research project will be completed in a period of 24 months.

The researcher [name] will register the patients, whether they are in the control group or in the intervention group. The physiotherapy intervention will be applied during 12 sessions from Monday to Friday to the selected patients.

The researcher [name] will be in charge of comparing the results with a double-blind system and thus comparing the results of the control group with the intervention group. The researcher [name] will be the methodological advisor in this research.

[name], with the help of [name] and [name] will write the results, discussion and conclusions of the project.

DISSEMINATION AND DISSEMINATION PLAN

- 1. Publication in journals indexed in the Journal Citation Report (JCR), in the field of Oncology and Rehabilitation and Physical Medicine and Physiotherapy.
- 2. Dissemination of results in national and international Congresses of Oncology and Rehabilitation and Physical Medicine and Physiotherapy.
- 3. Dissemination to the public, press releases and explanatory brochures of the project.
- 4. Dissemination on the website of the A.G.S. Campo de Gibraltar West.

ETHICAL ASPECTS OF THE RESEARCH

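### Previous shoulder disorder and bilateral breast surgery are neither excluded nor recorded, and no baseline-adjusted comparison is planned, so selective allocation could bias the main variables in either direction

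*Combined protocol and SAP*

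**What the plan says.** - **Eligibility** (Inclusion Criteria, Exclusion Criteria). Entry needs adult age, breast surgery, and the cord on the operated side: "Patient with lymphatic thrombus in the upper limb ipsilateral to the surgical intervention". The four exclusions are psychological, neurological, legal and metastatic.
- **Recorded variables** (Valuation Criteria). The list includes marital status, residence, children, smoking, sport, nodes removed, reconstruction and TNM stage. Surgery is recorded only as radical or conservative. There is no shoulder history and no unilateral/bilateral item.
- **Main variables** (Valuation Criteria; definitions under Control Group). These are shoulder goniometry, Constant and DASH. Range of motion is referred to fixed maxima: "flexion and abduction was 180°, for extension it was 45°, 100° for internal rotation and 80° for external rotation". The DASH is described as a "specific instrument for measuring the quality of life related to health problems to the upper limbs". The Constant score covers pain, daily activities, mobility and strength.
- **Timing** (Control Group, Intervention Group). Both groups are assessed at arrival and on days 30, 60 and 90.
- **Completion of treatment** (Description of the Intervention). Treatment may finish early, and for that "the patient must achieve the same ranges of motion and strength as the contralateral limb".
- **Design and analysis** (Type of Study, Analysis of Results). The study is quasi-experimental and gives no allocation rule. The analysis is descriptive by treatment group, with chi-square or Fisher tests for pairs of qualitative variables. For testing, "the significance level for all hypothesis testing is determined at 0.05".

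**The concern.** A stiff or operated shoulder that predates the breast surgery lowers goniometry, Constant and DASH results just as the cord does, but it does not resolve with the cord. A patient who has one may never reach the fixed maxima, whichever group she is in. If such patients are more common in one group, part of the difference between groups reflects shoulder history and not the manual therapy.

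Randomisation would make such differences a matter of chance. Here nothing says how patients come to be in one group or the other, so a systematic difference is possible. General objective I is to explore the magnitude of the effect, so a shift in group means bears directly on the study's aim. History that is not asked for at arrival cannot be relied on at analysis.

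**Working it through.** **Group size.** The plan states that "a random sample of 46 individuals in total would be enough to estimate". The target is a proportion of 10%, known to within 5 percentage points at 95% confidence; of the 2020 records it says the figure "has also been included adding 83 new patients". The finite-population formula is n = N z² p(1−p) / [d²(N−1) + z² p(1−p)], with N = 83, p = 0.10 and d = 0.05.
- z = 1.645: n = 45.06, rounded up to 46. This reproduces the plan.
- z = 1.96: n = 52.1, rounded up to 53. This does not.

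The figure 46 is used below only to fix the scale. Equal groups of 23 are an assumption, because no allocation ratio is given.

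**Shift per extra affected patient.** Assume a lasting loss of 60 degrees of abduction or 20 Constant points (neither is in the documents). One more affected patient in a group of 23 moves its follow-up mean by:
- 60/23 = 2.6 degrees
- 20/23 = 0.9 points

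With 4 affected in one group and 1 in the other, the gap is 3/23 × 60 = 7.8 degrees or 3/23 × 20 = 2.6 points.

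**What the arrival measurement removes.** Take the same 4 versus 1 split.
- *Deficit fully visible at arrival.* The arrival means differ by 7.8 degrees and the follow-up means by 7.8 degrees, so the mean changes differ by 7.8 − 7.8 = 0. Under ANCOVA with within-group slope b, (1 − b) × 7.8 degrees remains, which is small when b is near 1.
- *Deficit masked by the cord at arrival.* Suppose two patients both arrive at 100 degrees because of the cord. One can recover to 180, the other only to 120. Their gains are 80 and 20 degrees. The baselines are equal, so the whole 60 degrees stays in the change score and in ANCOVA. Only a history question identifies the second patient.

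**Chance versus selection.** Assumptions: 23 per group, 10–30% of patients affected, deficit of 10, 20 or 30 points on a 0–100 scale, within-group SD 15, no therapy effect, t-test on raw follow-up values at 0.05, 20,000 simulated studies per case.
- *Chance only.* The SD of the difference in prevalence is √(2p(1−p)/23), which is 9, 12 and 14 percentage points (rounded) at 10%, 20% and 30%. The probability that the groups differ by four or more affected patients is 8%, 19% and 26%. With 20% affected in both groups, the false-positive rate stays at about 5%.
- *Selection.* The expected spurious difference is (p₁ − p₂) × deficit, so 30% versus 10% with a deficit of 20 gives 0.20 × 20 = 4 points.

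| Prevalence in the two groups | Spurious difference for deficits of 10, 20, 30 | False-positive rate |
|---|---|---|
| 25% v 15% | 1, 2, 3 points | 6%, 7%, 8% |
| 30% v 10% | 2, 4, 6 points | 7%, 12%, 18% |
| 40% v 10% | 3, 6, 9 points | 10%, 22%, 34% |

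The sign depends on which group has more affected patients, so a real effect can be hidden as easily as a false one is created.

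**The opposite arm.** Listed goniometry covers only the affected limb, so a disorder of the other shoulder would not appear in the arrival data. It could change when the early-completion criterion is met, as could surgery on both sides. No effect of this on a main variable can be calculated from the documents.

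**The case against.** The strongest reply is that the main variables are measured at arrival in both groups and are to be described by treatment group. A reader might infer from the missing fields that an imbalance could be neither seen nor adjusted for. The documents do not support that: a fixed deficit is present at the first visit, shows as a baseline difference and largely cancels once the arrival value is used. This stands. It does not close the point, because Analysis of Results names no change-from-baseline or adjusted comparison of the quantitative variables, and a masked cap on recovery survives one.

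A reader might also infer that chance imbalance would pass for a therapy effect. It distorts a single estimate, but it is already in the standard error and leaves the false-positive rate at 5%. Bias needs selection, and the documents give no mechanism by which patients with shoulder disease would go to one particular group; they only leave it open.

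Three further replies stand in part.
- The inputs on frequency and size are assumed, and an excess of one patient gives only 2.6 degrees or 0.9 points.
- The contralateral reference governs only the early end of a three-week course and is not a listed outcome.
- The Constant form in Annex 1 has operation/diagnosis and side fields. These are neither a shoulder history nor a bilateral-surgery variable, and no analysis uses them.

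Finally, the study is exploratory, and other unrecorded factors could be raised in the same way. This one is worth singling out because it acts directly on all the main variables and costs two questions to record.

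**Conclusion.** The omission is confirmed: neither previous disorder or surgery of either shoulder nor bilateral breast surgery is excluded or recorded, while the main variables are not specific to the cord and the groups are not randomised. Two exposures remain. The first is a visible deficit left unadjusted, because the plan names no baseline-adjusted comparison. The second is a masked deficit, which such adjustment would not remove. Either can bias the estimated effect in either direction if allocation is selective; otherwise they add noise only.

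The size is not known. With 23 per group and a lasting loss of 60 degrees or 20 Constant points, all assumed, each extra affected patient in one group moves its follow-up mean by about 2.6 degrees or 0.9 points. The documents do not show that an imbalance exists or that it would be large. This is a cheap improvement to the plan and not a defect that invalidates the study.

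**What to change.** 1. At the first assessment in both groups, record previous disorder or surgery of either shoulder (yes/no, side) and whether breast surgery was unilateral or bilateral.
2. Tabulate both by group with the other arrival characteristics.
3. Pre-specify a comparison of the main variables adjusted for their arrival value, for example ANCOVA.
4. Repeat that comparison without the flagged patients as a sensitivity analysis.

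Steps 1 and 4 address the masked deficit; step 3 addresses the visible one. The cost is two questions per patient and one extra analysis, which will be imprecise if few patients are flagged. Eligibility, recruitment and the treatment-completion rule are left unchanged.
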